## 7.4.5.2. Action to be taken if partner pregnancy occurs

The investigator or designee should make every effort to collect pregnancy information on any female partner who is pregnant or becomes pregnant by a male subject during his participation in this study. The investigator, or his/her designee, should record pregnancy information on the appropriate form and submit this to GSK within 2 weeks of learning that a study subject's partner is pregnant, having first obtained the necessary written informed consent from the female partner directly. The subject's female partner should be followed to determine the outcome of the pregnancy. Information on the status of the

mother and child will be forwarded to GSK. Generally, follow-up will be no longer than 6 to 8 weeks following the estimated delivery date. Any premature termination of the pregnancy will be reported.

While pregnancy itself is not considered to be an AE or SAE, any pregnancy complication or elective termination of a pregnancy for medical reasons will be recorded as an AE or a SAE. A spontaneous abortion will always be reported as a SAE.

Any SAE occurring as a result of a post-study pregnancy (6-months after last dose) **and** considered reasonably related to the investigational product by the investigator will be reported to GSK. While the investigator is not obligated to actively seek this information in former study participants, he/she may learn of an SAE through spontaneous reporting.

See the Clinical Investigator Brochure and AVODART approved product label (if applicable) for additional details about dutasteride's potential effects on the male fetus.

## 7.4.6. Suicidality Monitoring

Assessment of suicidality will be performed using the C-SSRS which will be administered at baseline, during the course of study, and at the end of the study. Training to investigators and sites on suicidality assessment will be integral to the study implementation. Any AEs which, in the investigator's opinion, are possibly suicidality-related, will be recorded in the Possible Suicidality Related Adverse Event form (PSRAE); a supplemental CRF form designed to collect detailed information on the circumstances of reported AEs related to suicidality.

The 'baseline/screening' version of C-SSRS will be used at the pre-screening visit (V1a). The 'since last visit' version of C-SSRS will be used at Visits 4, 6 and 10 (6, 12 and 24 months post randomization respectively).

A trained rater will administer the C-SSRS questionnaires according to the schedule detailed in Table 1. The C-SSRS questionnaire will be completed during the clinical visit separately from the medical history and the standard adverse event questions.

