## STUDY DESIGN

This is a multicentre, randomized, double-blind, parallel group study. The aim of the study is to investigate whether combination therapy with dutasteride and tamsulosin is more effective than tamsulosin monotherapy for improvement of symptoms and health outcomes in a population of men at risk of BPH clinical progression including older men ( $\geq$ 50yrs), with moderate-severe symptoms of BPH, enlarged prostates ( $\geq$ 30cc) and PSA $\geq$ 1.5ng/mL.

Subjects who provide informed consent will be screened for inclusion into the study and eligible subjects will receive placebo tamsulosin and placebo dutasteride for four weeks. Following the four-week single-blind, placebo run-in period, each subject will be randomized to one of the following two treatment groups, according to a pre-determined randomisation schedule (1:1 ratio) for the double-blind phase of the study:

- Dutasteride 0.5mg once daily + tamsulosin 0.2mg once daily
- Dutasteride placebo once daily + tamsulosin 0.2mg once daily

Subjects will self-administer the study medication once daily for up to 104 weeks (2 years). Subjects will return to the clinic at 13 week intervals post-randomisation during the 2 year treatment period (i.e. at 13, 26, 39, 52, 65, 78, 91, and 104 weeks), for the assessments listed in the Time and Events Schedule, Section 7.

The total study duration for each subject will be up to 110 weeks, involving 11 scheduled visits. Due to the circadian changes in urinary flow measurements in BPH subjects, study visits for an individual subject should be conducted consistently in either the morning or afternoon hours to assess all urinary flow measurements.

Every effort will be made to ensure that all randomized subjects complete study assessments. The investigator and site staff are reminded that the subject should make every effort to adhere to all scheduled protocol visits/procedures and their associated windows. In circumstances where this is not possible, e.g. subject is on holiday and is late/early or even misses a study visit, this should be documented in the subject notes with reasons. The investigator should make every effort to ensure the subject always has sufficient study medication between study visits. If visit windows associated with each visit are utilized, the next visit should be scheduled in line with the randomisation baseline visit (Visit 2).

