## Suicidality

To protect subjects in the study, scores from C-SSRS tests will be reviewed in real time by the investigator and appropriate advice given to participants.

The C-SSRS scale has 10 outcomes, with binary (yes/no) responses. At the end of study, results will be assessed as follows:

- Suicidal ideation will be defined as a positive response at any time during treatment to any one of the five suicidal ideation questions (Categories 1-5) on the C-SSRS.
- Suicidal behavior will be defined as a positive response at any time during treatment to any one of the five suicidal behaviour questions (Categories 6-10) on the C-SSRS.
- Suicidal ideation or behavior will be defined as a positive response at any time during treatment to any one of the ten suicidal ideation and behaviour questions (Categories 1-10) on the C-SSRS.

The numbers of subjects with a positive response for suicidal ideation or suicidal behaviour will be reported at baseline and during study treatment at Visits 4, 6 and 10 (6, 12 and 24 months post randomization respectively). Scores on treatment will be compared with baseline scores and, for Visits 6 and 10, with scores at last visit to determine the incidence of treatment-emergent suicidality. An increase in C-SSRS total score to 4 or 5 will be considered as serious treatment-emergent suicidality. Due to the low numbers of subjects expected to exhibit suicidal behaviours, formal statistical testing will not be performed.

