#### Visit 1b (Placebo run-in)

Visit 1b should be conducted a maximum of 14 days after V1a (allowing sufficient time for lab results from V1a to be returned to site).

- 1. Review pre-screening PSA/laboratory results
- 2. Administer Problem Assessment Scale of the Sexual Function Index (PAS-SFI)
- 3. Perform physical examination, including digital rectal exam, qualitative breast examination, height, weight, and vital signs blood pressure and pulse after 5 mins sitting
- 4. Obtain a 12-lead electrocardiogram (after 5 mins supine)
- Assess SAEs
- 6. Measure peak urinary flow (if required)
- 7. Measure post void residual volume (if required)

- 8. Measure prostate volume by transrectal ultrasound (TRUS) if suitable TRUS not available
- 9. Review inclusion/exclusion criteria, including concomitant medications, and confirm patient eligibility
- 10. Call RAMOS
- 11. Dispense placebo run-in medication and provide dosing instructions
- 12. Schedule next clinic visit

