#### Visit 2 (Baseline/Randomisation)

Visit 2 should be conducted 28 days ( $\pm$  4 days) after Visit 1b. For each subject, all visits should be scheduled at a similar time of day: morning or afternoon. During Visit 2 the procedures listed below will be completed in the following sequential order:

- 1. Administer patient self-assessment questionnaires: International Prostate Symptom Score [IPSS], BHS Q8,BPH Impact Index [BII], Problem Assessment Scale of the Sexual Function Index (PAS-SFI)
- 2. Review concomitant medication and assess continuing eligibility
- 3. Record any episodes of AUR or prostatic surgical and minimally-invasive/non-surgical interventions along with associated resource utilization.
- 4. Record any episodes of UTI/urosepsis, urinary incontinence (first episode or consistent worsening), and renal insufficiency
- 5. Collect blood samples for PGx and HBsAG and Hepatitis C Antibody
- 6. Measure vital signs: blood pressure and pulse after 5 mins sitting
- 7. Assess AEs
- 8. Measure peak urinary flow
- 9. Measure post void residual volume
- 10. Call RAMOS to randomize subject
- 11. Collect unused placebo run-in medication and assess compliance
- 12. Dispense a 3-month supply (of blinded study medication and provide dosing instructions
- 13. Schedule next clinic visit

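### With no C-SSRS at Visit 2, the Month 6 'since last visit' form also covers screening and placebo run-in, so run-in ideation would be counted as treatment-emergent

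*Protocol*

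**What the plan says.** Protocol Section 7.4.6 says the C-SSRS is "administered at baseline, during the course of study, and at the end of the study". It then assigns the baseline/screening version to pre-screening Visit 1a and continues: "The 'since last visit' version of C-SSRS will be used at Visits 4, 6 and 10". Table 1 in Section 7 agrees, marking the C-SSRS at Visits 1a, 4, 6 and 10 only. Appendix 2 introduces the randomisation visit with "During Visit 2 the procedures listed below will be completed in the following sequential order", and the list that follows repeats the IPSS, BHS, BII and PAS-SFI but has no C-SSRS.

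On analysis, Section 9.3.7.2.1 states: "Suicidal ideation will be defined as a positive response at any time during treatment" to any of the five ideation questions, and it defines behaviour in the same way. It reports Visits 4, 6 and 10 as on-treatment. It derives treatment-emergent suicidality by comparing scores with baseline and, at Visits 6 and 10, also with the score at the last visit. Section 9.3.7 defines baseline as the last assessment before randomised treatment starts, which for this instrument is Visit 1a. No rule refers to the date an event began.

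On timing, Appendix 2 says "Visit 1b should be conducted a maximum of 14 days after V1a", and "Visit 2 should be conducted 28 days" after Visit 1b, with 4 days' latitude either way. Section 3 says: "Subjects will return to the clinic at 13 week intervals post-randomisation during the 2 year treatment period". Section 7.2.2 allows 14 days either side of each post-baseline visit.

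**The concern.** A since-last-visit form takes its meaning from the previous administration. Here that was at pre-screening, before the placebo run-in had begun, and the analysis treats whatever is reported at Visit 4 as belonging to treatment. A man with no ideation at Visit 1a who has ideation during single-blind placebo and then reports it at Visit 4 is negative at baseline and positive 'during treatment'. Under Section 9.3.7.2.1 he is a treatment-emergent case, although the episode preceded his first randomised dose.

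Suicidality is a listed safety endpoint (Section 7.3.1). Section 7.3.9 adds the assessment because dutasteride is regarded as active in the central nervous system. The protocol expects few cases, so each misdated case counts in a table of small numbers. If onset relative to first dose is not collected with the questionnaire, the Reporting and Analysis Plan (RAP) cannot reliably reconstruct it afterwards. A second, smaller problem is that Section 7.4.6, which directs raters, does not say what 'last visit' refers to, and clinic visits without a C-SSRS lie between those with one.

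**Working it through.** **Inputs.** Visit 1a to 1b: up to 14 days (Appendix 2; Table 1 shows V1a + 14 days). Visit 1b to 2: 28 days, range 24 to 32 (Appendix 2). Visit 2 to 4: 26 weeks = 182 days, range 168 to 196 (Table 1; Section 7.2.2). First randomised dose is taken to be at Visit 2, when double-blind medication is dispensed.

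**Timeline check.** 14 + 28 + 104 × 7 = 770 days = 110 weeks. Visits 1a, 1b and 2 to 10 make 2 + 9 = 11. Both match the study duration and visit count in Section 3.

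**What 'last visit' can mean.** Section 9.3.7.2.1 compares Visits 6 and 10 with scores at the last visit. The clinic visits immediately before them are Visits 5 and 9, which have no C-SSRS in Table 1 and hence no score. In the analysis text, therefore, 'last visit' can only mean the last visit with a C-SSRS. Applied to Visit 4, the previous C-SSRS is the one at Visit 1a.

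**Pre-treatment share of the Visit 4 recall window.** Share = P / (P + T), where P is days from Visit 1a to Visit 2 and T is days from Visit 2 to Visit 4.

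- Nominal: P = 14 + 28 = 42, T = 182; 42 / 224 = 18.75%, about 19%.
- Longest P, nominal T: P = 14 + 32 = 46; 46 / 228 = 20.2%.
- Longest P, earliest Visit 4: T = 168; 46 / 214 = 21.5% (0.2150 before rounding; 21% if rounded down from 21.495).
- The 14 days are a maximum. If the gap from 1a to 1b approached zero, P would be 28 and the share 28 / 210 = 13.3%. This is a limit only, because laboratory results must return before Visit 1b.

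These are shares of recall time, not misclassification rates. The documents give no event rate from which to calculate the latter.

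**Following one case through the rules.**

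1. Visit 1a: negative. This is the baseline (Section 9.3.7).
2. Run-in: ideation occurs, and no C-SSRS is scheduled.
3. Visit 2: randomisation, with no C-SSRS (Appendix 2).
4. Visit 4: the form asks about the time since the last C-SSRS; the answer is positive.
5. Section 9.3.7.2.1: counted as on-treatment, and as treatment-emergent because it exceeds the Visit 1a score.

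Nothing in these steps requires the onset to be dated.

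**After the change.** With a C-SSRS at Visit 2 and 'last visit' defined as the previous C-SSRS, P at Visit 4 falls to 0 days. Visits 4, 6 and 10 then cover 26 + 26 + 52 = 104 of 104 treatment weeks.

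**The case against.** The strongest reply has four parts.

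First, a screening-visit baseline is this protocol's normal practice. PSA, laboratory tests and prostate volume also take their baseline from Visit 1a or 1b, and Section 7.4.6 says which C-SSRS form is used there. This stands: the reference to baseline is not in itself a contradiction. What sets the C-SSRS apart is that its next form looks back across the interval.

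Second, run-in episodes occur on placebo before randomisation, so they should balance between arms, and no formal test is planned. This also stands, and it limits the harm to descriptive counts.

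Third, other safeguards exist. A reader might infer that nobody checks suicidality between Visit 1a and randomisation. The documents do not support that. AEs are collected from the start of the run-in (Section 7.4.7) and assessed at Visit 2 before the randomisation call (Appendix 2). Possible suicidality-related AEs go on the PSRAE form (Section 7.4.6). Early discontinuers also have a C-SSRS at the End of Study Treatment visit (Section 7.2.2.5), although its version and recall period are not stated. None of this repairs the C-SSRS endpoint, which Section 9.3.7.2.1 defines by C-SSRS responses alone.

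Fourth, the handling of onset could be left to the RAP, to which Section 9.3.7.2 defers the details of safety analyses. This stands only in part: the RAP can set the rule, but it needs the timing to have been collected.

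A reader might also infer, taking 'last visit' as the previous clinic visit, that the forms reach back only 13 weeks each and so miss most on-treatment events. The comparison with last-visit scores in Section 9.3.7.2.1 does not fit that reading, and weeks outside a form's recall are not missed events when AE and PSRAE collection runs throughout. What remains is that raters are given no definition.

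**Conclusion.** The point holds in this form. Followed as written, the plan counts ideation or behaviour first arising in screening or placebo run-in, and reported at Visit 4, as occurring on treatment and as treatment-emergent. About 19% of the Visit 4 recall window (42 of 224 days), and at most about 21% (46 of 214), lies before randomised treatment. The share is lower where Visit 1b follows Visit 1a by less than 14 days.

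The conclusion rests on 'last visit' meaning the last C-SSRS, on first dose at Visit 2, and on no onset date being collected with the C-SSRS response, since the protocol describes none. The consequence is inflated descriptive safety counts in both arms. It does not systematically favour either arm and does not touch the primary efficacy result. The change should be made because it is specific and cheap, and because the information is hard to recover once the forms have been completed.

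**What to change.** 1. In Section 7.4.6, state that 'since last visit' means since the previous C-SSRS administration.
2. At Visit 4, or at the End of Study Treatment C-SSRS if that comes earlier, record for any positive response whether it began before or after the first randomised dose. State which form version and recall period apply at the End of Study Treatment visit.
3. In Section 9.3.7.2.1, count as on-treatment or treatment-emergent only responses with onset after the first randomised dose, and show earlier onset separately as pre-treatment.

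This costs one eCRF field and a few sentences of protocol text.

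An alternative to item 2 for scheduled visits is to give the since-last-visit form at Visit 2, before the RAMOS randomisation call, and add it to Table 1 and Appendix 2. That closes the pre-treatment period directly, at the cost of one extra short questionnaire at an existing visit by a trained rater. The definition in item 1 is needed either way.

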## 7.4.7. Time Period and Frequency of Detecting AEs and SAEs

The investigator or site staff is responsible for detecting, documenting and reporting events that meet the definition of an AE or SAE.

AEs will be collected from the start of the placebo run-in phase until the end of the two year study period.

SAEs will be collected over the same time period as stated above for AEs. However, any SAEs assessed **as related** to study participation (e.g., investigational product, protocolmandated procedures, invasive tests, or change in existing therapy) or related to a GSK concomitant medication, will be recorded from the time a subject consents to participate in the study up to the end of the two year study period. All SAEs will be reported to GSK within 24 hours, as indicated in Section 7.4.8.

After discontinuation of study treatment, the investigator will monitor all AEs/SAEs that are ongoing until resolution or stabilization of the event or until the subject is lost to follow-up. Investigators are not required to actively seek information on adverse events occurring after the follow-up contact, but may report any adverse event that they believe may be related to investigational product regardless of when the event occurs.

# 7.4.8. Prompt Reporting of Serious Adverse Events and Other Events to GSK

SAEs, partner pregnancies, and liver function abnormalities and any other events meeting pre-defined criteria will be reported promptly by the investigator to GSK as described in the following table once the investigator determines the event meets the protocol definition for that event.

	Initial Reports		Follow-up Information on a Previous Report	
Type of Event	Time Frame	Documents	Time Frame	Documents
All SAEs	24 hours	SAE data	24 hours	Updated SAE data
		collection tool		collection tool
Partner Pregnancy	2 Weeks	Pregnancy	2 Weeks	Pregnancy Follow
		Notification Form		up Form
ALT≥3xULN and bilirubin ≥2xULN (>35% direct) (or ALT≥3xULN and INR>1.5, if INR measured) ²	24 hours 	SAE data collection tool.	24 hours	Updated SAE data collection tool.

- 1. GSK to be notified at onset of liver chemistry elevations to discuss subject safety.
- 2. INR measurement is not required; if measured, the threshold value stated will not apply to subjects receiving anticoagulants.

The method of detecting, recording, evaluating and follow-up of AEs and SAEs plus procedures for completing and transmitting SAE reports to GSK are provided in the SPM. Procedures for post-study AEs/SAEs are provided in the SPM.

## 7.4.9. Regulatory reporting requirements for SAEs

Prompt notification of SAEs by the investigator to GSK is essential so that legal obligations and ethical responsibilities towards the safety of subjects are met.

GSK has a legal responsibility to notify both the local regulatory authority and other regulatory agencies about the safety of a product under clinical investigation. GSK will comply with country specific regulatory requirements relating to safety reporting to the regulatory authority, Institutional Review Board (IRB)/Independent Ethics Committee (IEC) and investigators.

Investigator safety reports are prepared for suspected unexpected serious adverse reactions according to local regulatory requirements and GSK policy and are forwarded to investigators as necessary.

An investigator who receives an investigator safety report describing a SAE(s) or other specific safety information (e.g., summary or listing of SAEs) from GSK will file it with the IB and will notify the IRB/IEC, if appropriate according to local requirements.

#### 7.5. Health Outcomes

## 7.5.1. BPH-related Quality of Life

The effect of study treatment on BPH-related quality of life will be assessed using three self-administered questionnaires: the BPH-related health status (question 8 of IPSS); the BPH Impact Index (BII) and Problem Assessment Scale of the Sexual Function Index (PAS SFI). Each questionnaire is briefly described below and will measure impact of BPH symptoms, health-related quality of life and sexual function.

#### a. International Prostate Symptom Score (IPSS) [Badia, 1997; Barry, 1992]

The IPSS is a 7 item instrument (essentially the same as the American Urological Association Symptom Index, AUA-SI) designed to quantify urinary symptoms but with an additional, independent eighth question BPH on quality of life (see Appendix 5). The IPSS will be administered at Pre-screening (Visit 1a), at Baseline (Visit 2) after completion of the placebo run-in period and at every 13 week clinic visit thereafter during the study treatment period. At Pre-screening (Visit 1a), subjects with IPSS <12 points (based on the first 7 questions) should be excluded from the study

## b. BPH Impact Index (BII) [Barry, 1995]

The BII is a 4 item instrument which assesses the overall impact of BPH on a patient's general sense of well being and measures aspects of physical discomfort, worry and bother, all of which can be affected by BPH and its symptoms (See Appendix 6).

The BII will be administered at Pre-screening (Visit 1a), at Baseline (Visit 2) after completion of the placebo run-in period and at every 13 week clinic visit thereafter during the study treatment period.

# c. Problem Assessment Scale of the Sexual Function Inventory (PAS-SFI) [O'Leary, 1995]

Because BPH and subsequent medical treatments may potentially affect sexual functioning, a brief Sexual Function Index will be included in this trial to capture information about various aspects of patients' sexual functioning [O'Leary, 1995] (See Appendix 6). The PAS-SFI will be administered at screening (visit 1b, during (Baseline) Visit 2 after completion of the placebo run-in, then annually thereafter following randomization.

#### 7.5.2. Questionnaire administration

The subject will complete self-administered questionnaires according to the schedule detailed on the Time and Events Table.

The investigator will ask the study subject to complete a questionnaire during the clinical visit separately from the medical history and the standard adverse event questions.

Questionnaires should be completed in a quiet place (preferably the same place each time, if possible), and at as consistent a time during the study visit as possible. To avoid biasing responses, subjects should not be told the results of diagnostic tests prior to completing the questionnaire. Regardless of when the questionnaire is completed, the subject should be given adequate time to complete all items. No stated or implied time limit for completing the questionnaire items will be given.

The subject should be asked to complete the questionnaires as completely and as accurately as possible. If the subject requests help or clarification of any question, he should be asked to read the instructions again and to give the best answer possible to each question. Subjects should be encouraged to report their own experiences and opinions. The investigator will not provide the subject with an answer to any question nor interpret any portion of the question.

